three-pronged approach to the COMprehensive Intensive REhabilitation Program after STROKE (COMIRESTROKE): **COMIRESTROKE** – **ICF**, the mostly individualized approach implementing the International Classification of Functioning, Disability and Health (ICF) model with aim to improve an individual's recovery (rather than impairment) through effective management of care (14); **COMIRESTROKE** – **TECH**, approach implementing technology-based PT" and **COMIRESTROKE** – **NEFI**, approach implementing neuroproprioceptive "facilitation and inhibition" PT.

There is very limited evidence to guide judgements regarding the rehabilitation potential following stroke (17-20). Research shows that some clinical features such as the level of consciousness, severity of hemiplegia, incontinence, dysphagia and dysphasia (21) or disease severity (22, 23) may be considered as indicators as to whether the rehabilitation process could be effective. However, confusion between predicting natural unassisted recovery and predicting responsiveness to targeted rehabilitation still remains (17). Moreover, prediction models of rehabilitation potential have never been fully and properly prospectively tested. The models considered by Prabhakaran et al., 2008 were only able to explain 47% of the variance in recovery after stroke with 53% of the variance remaining unaccounted (24). Nowadays focus shifted from the determination of rehabilitation potential to identifying clear indicators of effective rehabilitation including molecular biological readouts (25). This is reason why a wide range of patient characteristics will be collected. We consider, the patients' subjective feelings about how they have improved to be the most important aspect. Therefore, the Goal Attainment scale (GAS) together with the Patient-reported Outcomes Measurement Information System (PROMIS) Global Health, and the World Health Organization Disability Assessment Schedule (WHODAS 2.0) were chosen as primary outcomes. As secondary outcomes, measurements will be taken of motor, cognitive, psychological, speech and swallowing functions as well as functional independence.

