2.1. Clinical trial design

This will be a Four-Arm Parallel-Group Randomised Double Blinded Controlled Trial with a longitudinal design. Patients who fulfilled inclusion criteria will be randomly assigned to one of the four research groups (Group 1, 2, 3 or 4). Three groups will undergo an inpatient COMIRESTROKE (4 hours/day for 3 weeks). Group 1 (COMIRESTROKE – ICF) will undergo individualised rehabilitation therapy embodying the ICF system as a therapeutic tool, where current needs and wishes of the person after IS are integrated into an interdisciplinary team rehabilitation programme management. Group 2 and 3 will undergo a standard comprehensive intensive rehabilitation program three hours per day (39) plus one hour of specific PT (an individual neuroproprioceptive "facilitation inhibition" for Group 2, a technology-based training for Group 3). Group 4 will undergo standard care and will serve as comparative one to the intensified intervention groups.

Participants will be examined four times (Figure 1). At the beginning and after three weeks of hospitalization (both primary, secondary outcomes and a blood draw will be obtained for total RNA extraction, cDNA synthesis and real-time QPCR assessment of lncRNA candidates previously identified as potential therapeutic influencers in ischemic stroke), and then three months and one year after the end of the program (primary outcomes only).

Figure 1: Design of the study

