2.6. Estimated size

It is estimated that approximately 110 people will be recruited to the clinical trial each year. This number is based on the fulfilment of performance and quality indicators report of cerebrovascular care at the Centre for Highly Specialized Patient Care for Stroke Patients at Thomayer Hospital 2019. A total of 210 people is expected to be enrolled in the clinical trial over a period of two years (Figure 2), corresponding to a required sample number of 70 patients per group. This value is necessary in order to detect a significant difference in improvement

between two groups when achieving a mean difference effect (Cohen's d = 0.5), a significance level of $\alpha = .05$ and a strength of $1-\beta = .80$. The sample size was determined based on the minimal clinically significant change on a Berg balance scale (96).

Figure 2: Planned recruitment and randomisation process

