2.8. Hypotheses

This clinical trial will test the following scientific hypotheses:

I. COMIRESTROKE under all three settings has a positive influence on all outcomes and higher effect than control group.

II. COMIRESTROKE - ICF will have the highest impact on primary outcomes (GAS, PROMIS, WHODAS 2.0) and on such secondary outcomes that were identified as treatment goals. Furthermore, we expect the highest impact on the primary outcomes in the follow-up (three and twelve months after finishing the rehabilitation).

III. COMIRESTROKE – NEFI will have the highest effect on the secondary outcomes, mainly on motor functions. Moreover, it will most significantly lead to the initiation of plastic and adaptive processes, assessed by the level of lncRNAs in the peripheral blood.

IV. The most important predictor of effective rehabilitation will be the level of disability at admission time; however, the content of the rehabilitation will have an impact on perceived, clinical, and physiological changes of the rehabilitant.

The exploratory goals of this clinical trial are as follows:

Goal I - Improvement patterns: Considering the high number of measured outcomes, for a deeper understanding of therapy efficacy with respect to patient and treatment characteristics, this clinical trial will aim to identify groups of patients with similar improvement patterns post therapy.

Goal II - Item-level analysis: To provide a deeper understanding of the differences in effectiveness between the three therapeutic approaches, this clinical trial will plan to explore item-level between-group differences in improvement.

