2.9. Measuring the effectiveness of rehabilitation

To test hypothesis I., i.e., a positive influence on all outcomes, the effect of therapy for each therapeutic group will be assessed separately by paired t-tests performed on pre-test and post-test scores. The Wilcoxon rank test will be used on data where normal distribution cannot be expected.

To test hypotheses II. and III, a comparison between therapeutic groups will be performed using two sample Student t-tests on differences between measurement time points (or Wilcoxon tests respectively for data, where normal distribution of the differences cannot be expected). For hypothesis II, the COMIRESTROKE - ICF group will be compared against the rest of the participants. For hypothesis III, the COMIRESTROKE - NEFI group will be compared against the rest of the participants. A one-sided alternative will be tested according to our hypotheses. We will also implement the one-way ANOVA test to jointly compare all three groups for prepost differences. In addition, a Tukey post-hoc comparison will be made to detect any further group differences beyond our hypotheses.

To assess the overall impact of rehabilitation and to compare effectiveness of different therapeutic approaches for Hypotheses I – III in more complex way, and to test for effect of other covariates in Hypothesis IV, a linear mixed effect model will be used with random patient effect fitted to longitudinal patient data. Measurement effect, group effect and their interaction, as well as effects of other covariates such as the level of disability in admission time will be tested by F test.

To address Goal I, correlations between changes in different examination scores will be evaluated using Pearson correlation coefficient and its nonparametric analogies. A cluster analysis will be performed to identify different phenotypes. This will allow the identification of different groups of patients in relation to the efficacy of the neuro-rehabilitation programs.

To address Goal II, for selected multi-item instruments, item-response theory (IRT) and generalized linear regression models will be used to study differential item functioning with respect to rehabilitation groups. Account will be taken for other respondent characteristics. Use will be made of differential item functioning in change (DIF-C) analysis (7) in order to detect between-group differences.

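### The 80% power in section 2.6 rests on the Berg Balance Scale, so it has no support for the primary outcomes or the follow-up, and four arms do not deliver it for a two-arm comparison

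*Combined protocol and SAP*

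**What the plan says.** - **Sample size (2.6).** 210 patients in total, said to correspond to 70 per group, to detect a difference in improvement "between two groups when achieving a mean difference effect (Cohen's d = 0.5"), with alpha .05 and power .80. The basis is given in one sentence: "The sample size was determined based on the minimal clinically significant change on a Berg balance scale". Neither the BBS change nor its SD is stated, and no allowance for loss is stated.
- **Primary outcomes (1 and 2.5.1).** GAS, PROMIS Global Health and WHODAS 2.0. The Introduction says that the first two, together with "the World Health Organization Disability Assessment Schedule (WHODAS 2.0) were chosen as primary outcomes".
- **BBS (2.5.2.1 and Table 2).** Listed among the secondary physical-function measures and marked at baseline and +3 weeks only.
- **Follow-up (2.1).** Assessments at the start and after three weeks, "and then three months and one year after the end of the program (primary outcomes only").
- **Hypothesis II (2.8).** ICF is expected to do best on the primary outcomes, and: "Furthermore, we expect the highest impact on the primary outcomes in the follow-up", at three and twelve months.
- **Analysis (2.9).** For Hypotheses II and III, two-sample t-tests on changes compare one arm with all other participants. "A one-sided alternative will be tested according to our hypotheses". Comparisons between individual arms appear as a Tukey post-hoc step.
- **Allocation (2.2).** Four arms, 1:1:1:1.

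**The concern.** The power statement and the trial's main question concern different outcomes and different times. The figure of 0.5 SD is justified only by a balance scale that stops at week 3. The conclusions will rest on self-reported health, self-reported disability and individual goal ratings, up to a year later. Nothing in the documents says that 0.5 SD is a plausible or important difference on those measures, or that it would persist to 12 months with the patients still in follow-up.

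What is at stake is interpretation. A null result on PROMIS, WHODAS or GAS, above all at 12 months, would be read against an 80% power that was never established for it. Readers could not tell an absent effect from one that the trial could not detect. The figure is also a two-group figure, while the patients are divided among four arms.

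**Working it through.** **Inputs from the documents:** d = 0.5, alpha .05, power .80, 70 per group, 210 in total (2.6); four equal arms (2.2); one arm against the rest, one-sided (2.9). **Assumptions:** loss of 0%, 10% or 20%, equal across arms; d = 0.5 carried over to a primary outcome, with 0.4 and 0.3 as alternatives; the rest means all three other arms. Section 2.6 does not say whether alpha is one- or two-sided, so I take two-sided for two arms.

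**1. The plan's own figure.** Per group, n = 2(z₁₋α/₂ + z₁₋β)²/d² = 2(1.960 + 0.842)²/0.25 = 62.8, so 63 (64 by the exact t calculation). One-sided, with 1.645 in place of 1.960, it is 50 (51 by t). Neither gives 70. At 70 per group the two-sided power is 84%. A figure of 70 appears if an unstated 10% loss is added: 63/0.9 = 70.

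**2. Patients per arm.** 210/3 = 70, but 210/4 = 52.5. Four arms of 70 would be 280.

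**3. Two arms, two-sided.** Power ≈ Φ(d√(n/2) − 1.960). For n = 52.5: 0.5 × 5.123 = 2.562; 2.562 − 1.960 = 0.602; Φ = 72.6%, or 71.8% by the exact t. The detectable difference at 80% is about 2.802/5.123 = 0.55 SD.

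**4. ICF against the rest, one-sided.** Power ≈ Φ(d√(n₁n₂/(n₁+n₂)) − 1.645). For 52.5 v 157.5: 52.5 × 157.5/210 = 39.375, with root 6.275; 0.5 × 6.275 = 3.137; 3.137 − 1.645 = 1.492; Φ = 93.2%, or 93.1% by the exact t. The detectable difference is about 2.487/6.275 = 0.40 SD.

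Exact t results at d = 0.5:

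| Assumed loss | Per arm | Two arms, two-sided: power | Detectable at 80% | ICF v rest, one-sided: power | Detectable at 80% |
|---|---|---|---|---|---|
| 0% | 52.5 | 72% | 0.55 SD | 93% | 0.40 SD |
| 10% | 47 | 67% | 0.58 SD | 91% | 0.42 SD |
| 20% | 42 | 62% | 0.62 SD | 87.5% | 0.44 SD |

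**5. If d is smaller on a primary outcome (no loss).** At d = 0.4, power is 53% for two arms and 80% for ICF against the rest. At d = 0.3 it is 33% and 59%.

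**6. What cannot be computed.** No required sample size for GAS, PROMIS or WHODAS 2.0 can be derived, because the documents give no difference or SD for them. The step from the BBS change to d = 0.5 cannot be checked either, for the same reason.

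**The case against.** The strongest reply is that Cohen's d is scale-free. The arithmetic in 2.6 holds for any outcome with a true standardised difference of 0.5, so choosing BBS changes none of the figures. The drop to 72% comes only from dividing 210 by four. Moreover, the test that 2.9 plans for the primary outcomes pools three arms and is one-sided, and it has 93% power at d = 0.5 and about 88% after 20% loss.

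Most of this stands, and it limits the point. A reader might infer that the primary outcomes are underpowered. The documents do not show that: the planned test is well powered if d = 0.5 holds, and whether it holds is unknown. Scale-freeness does not supply the missing support, since 2.6 justifies 0.5 by BBS alone. The four-arm shortfall is a separate cause, but it affects the same stated figure.

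Three other inferences also go too far.

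- **That the calculation belongs to no planned test.** Hypothesis III covers the secondary outcomes, chiefly motor function, and 2.9 gives it two-sample t-tests on change. BBS falls under these, although it is not singled out.
- **That loss was ignored.** No allowance is stated, but 70 against 63 leaves room for an unstated 10%.
- **That the 80% is at least right for BBS at week 3.** At d = 0.5, two-sided, it is 72% with 52–53 per arm and 84% with 70.

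**Conclusion.** The point holds as a lack of support. The only power statement comes from a secondary outcome that is not measured after week 3, and nothing is offered for the primary outcomes or for the follow-up comparisons of Hypothesis II. In addition, the stated 80% is not what 210 patients in four equal arms give for two arms at d = 0.5. That comparison has 72%, or 62–67% with 10–20% loss; the Tukey step in 2.9 adjusts for multiplicity, so an unadjusted t-test flatters it. For the planned ICF-versus-rest test, power runs from 93% at d = 0.5 to 59% at d = 0.3 without loss, so the answer depends almost wholly on an effect size that the plan does not justify. The loss rates, the alternative values of d and the use of d = 0.5 for the primary outcomes are assumptions, not figures from the documents.

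**What to change.** Amend section 2.6, without enrolling more patients:

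1. Replace the single 80% with the power, or the detectable difference in SD units, for GAS, PROMIS and WHODAS 2.0 at week 3, 3 months and 12 months. Use the actual four-arm numbers, the test named in 2.9 with its sidedness, and a stated loss rate.
2. Say that d = 0.5 was taken from BBS and is an assumption for the primary outcomes.
3. Reconcile 210 and 70 per group with the four arms of section 2.2, and state whether 70 includes an allowance for loss.

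There is no need to reattach the 80% to BBS, which would keep a figure that neither group size yields, or to make BBS the lead outcome for Hypothesis III, which is a matter of preference.

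The cost is a rewritten paragraph. Detectable differences in SD units need no outside data, so this can be done before any results are known. Treatment, visits and data collection do not change. The price is a less favourable power statement for comparisons between two arms, and an open admission that the effect size on the primary outcomes is assumed.

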2.7. Descriptive statistics

On the baseline, the distribution of all primary and secondary outcomes will be visualized using histograms and QQ plots. We expect normal distributions in most of the variables defined as raw scores from appropriate tests, or in their log transformations (e. g. tests measuring time needed to walk certain distance or to perform a task). The groups will be compared in their characteristics, primary, and secondary outcomes using the one-way analysis of variance (ANOVA), and its nonparametric version (Kruskal – Wallis test), where needed. The Benjamini-Hochberg correction (97) will be used to account for multiple comparisons. We expect no differences between groups on the baseline. If differences are observed, these will be accounted for in the longitudinal models.

2.8. Hypotheses

This clinical trial will test the following scientific hypotheses:

I. COMIRESTROKE under all three settings has a positive influence on all outcomes and higher effect than control group.

II. COMIRESTROKE - ICF will have the highest impact on primary outcomes (GAS, PROMIS, WHODAS 2.0) and on such secondary outcomes that were identified as treatment goals. Furthermore, we expect the highest impact on the primary outcomes in the follow-up (three and twelve months after finishing the rehabilitation).

III. COMIRESTROKE – NEFI will have the highest effect on the secondary outcomes, mainly on motor functions. Moreover, it will most significantly lead to the initiation of plastic and adaptive processes, assessed by the level of lncRNAs in the peripheral blood.

IV. The most important predictor of effective rehabilitation will be the level of disability at admission time; however, the content of the rehabilitation will have an impact on perceived, clinical, and physiological changes of the rehabilitant.

The exploratory goals of this clinical trial are as follows:

Goal I - Improvement patterns: Considering the high number of measured outcomes, for a deeper understanding of therapy efficacy with respect to patient and treatment characteristics, this clinical trial will aim to identify groups of patients with similar improvement patterns post therapy.

Goal II - Item-level analysis: To provide a deeper understanding of the differences in effectiveness between the three therapeutic approaches, this clinical trial will plan to explore item-level between-group differences in improvement.

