Ischemic stroke causes an extensive range of clinical dysfunctions. To narrow the program, motor disability was chosen as one of the inclusion criteria, as it is the most common and widely recognised problem (8). Motor recovery provides a direct means of addressing the effectiveness of therapy. Nineteen intervention types relevant to motor recovery after stroke have been identified (8). The most commonly applied include those involving Motor/Skill acquisition and Technology-based individualized interventions where the patient is increasingly active in the motor re-training process and the principles of sensory-motor learning are applied. Neurophysiological approaches including Bobath which stimulate neuroproprioceptive "facilitation, inhibition" (106, 107), are rarely utilised. In the Czech Republic, Vojta reflex locomotion, is routinely used in clinical practice. To date, only one very recent study has documented its effectiveness in stroke patients (108). This clinical trial should confirm this promising finding, and moreover enable the comparison of its effectiveness with alternative rehabilitation approaches implementing technology-based physiotherapy as well as those applying the ICF model. Importantly, this clinical trial will enable the systematic collection of demographics, biometric and molecular marker information allowing an opportunity for association analysis that may provide further evidence identifying indicators of effective rehabilitation. It is expected that the treatment will be much more effective in patients who start the rehabilitation soon after the ischemic stroke event. Patients will be scored for disability, personality traits, cardiovascular function and cognitive ability as outlined above.

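### Hypothesis IV ranks admission disability first among predictors, but the plan only tests whether each covariate effect is non-zero and gives no rule for the ranking

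*Combined protocol and SAP*

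**What the plan says.** Section 2.8 opens with "This clinical trial will test the following scientific hypotheses" and keeps these apart from the exploratory goals that follow. Hypothesis IV is the fourth of them: "The most important predictor of effective rehabilitation will be the level of disability at admission time". A second clause adds that the content of rehabilitation will also matter.

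Section 2.9 gives the analysis: "to test for effect of other covariates in Hypothesis IV, a linear mixed effect model will be used with random patient effect". The terms are "Measurement effect, group effect and their interaction", and then "effects of other covariates such as the level of disability in admission time will be tested by F test". The covariates are not listed beyond that one example.

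Several candidate rivals are measured. The Introduction says of the search for indicators of effective rehabilitation: "This is reason why a wide range of patient characteristics will be collected". Section 2.4 lists age, days since stroke, NIHSS, pre-stroke mRS, MoCA and NEO-FFI. The Discussion (section 3) itself points to one rival, expecting that "the treatment will be much more effective in patients who start the rehabilitation soon" after the stroke.

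**The concern.** An F test of a covariate asks whether its effect is zero. Hypothesis IV asks a different question: whether one predictor outweighs all the others. A ranking has meaning only against a stated set of competitors, on a stated scale, with a stated rule for deciding that the leader is really ahead. The plan gives none of these.

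One aim of the trial is to find indicators of effective rehabilitation. If disability were reported as the leading predictor because its test was significant, another measured characteristic that predicts recovery better could be passed over. If no such claim were made, a numbered hypothesis would simply go unanswered.

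**Working it through.** **1. Does any planned analysis compare predictors?**

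- Hypothesis IV analysis (2.9): one F test per effect. No importance measure, contrast between predictors or decision rule is given.
- Goal I (2.9): "correlations between changes in different examination scores will be evaluated using Pearson correlation coefficient", followed by clustering of patients. This relates outcome changes to each other, not baseline predictors to outcome.
- Goal II (2.9): item-level differential functioning between rehabilitation groups.
- Discussion (section 3): mentions an association analysis, without a method.

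None of these produces the ranking. The only interaction named in the mixed model is group by measurement. A main effect of disability would therefore describe the level of the outcome rather than its improvement. Adding a disability-by-measurement term would cure that, but would still show only that disability matters, not that it matters most.

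**2. How small an effect is significant?**

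The plan has no figure for Hypothesis IV. The total of 210 comes from section 2.6, where it serves a two-group comparison. In a regression with two predictors there are 210 - 3 = 207 residual degrees of freedom and the two-sided 5% critical value is t = 1.971. The smallest significant partial correlation is t/√(t² + 207) = 1.971/√(3.887 + 207) = 0.136, or 0.136² = 1.8% of residual variance. Significance is a low bar compared with being first.

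**3. How often is a truly second-ranked disability effect significant?**

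All coefficients here are assumptions, because the documents give none. Let b be the standardised coefficient of disability, c that of one rival, ρ their correlation (0 to 0.5), and let the outcome variance be 1. Approximately,

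P(significant) = Φ( b√(N(1 - ρ²)) / √(1 - b² - c² - 2bcρ) - 1.971 ).

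Example with b = 0.10, c = 0.20, ρ = 0: 0.10 × 14.49/√0.95 = 1.487, and Φ(1.487 - 1.971) = 0.31. With ρ = 0.5: 0.10 × 12.55/√0.93 = 1.301, and Φ(-0.670) = 0.25.

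| Disability v rival | Formula, ρ = 0 | Formula, ρ = 0.5 | Simulated range |
|---|---|---|---|
| 0.10 v 0.20 | 31% | 25% | 25-31% |
| 0.15 v 0.25 | 62% | 52% | 51-61% |
| 0.20 v 0.40 | 90% | 84% | 83-90% |
| 0.25 v 0.35 | 98% | 96% | 95-98% |

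The simulations used 4,000 trials per setting. At 0.25 v 0.35, disability had the larger test statistic in only 13-20% of trials; at 0.20 v 0.40, in 1-5%. With equal coefficients (0.30 v 0.30) it was significant in at least 99% of trials and came first in about half. At moderate coefficients, then, significance carries almost no information about rank.

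**4. Could a ranking rule succeed when disability really is first?**

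For uncorrelated predictors a direct contrast has z = (b - c)/√(2(1 - b² - c²)/N).

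- 0.40 v 0.30: 0.10/√(2 × 0.75/210) = 0.10/0.0845 = 1.18; Φ(1.18 - 1.97) is about 0.21.
- 0.40 v 0.20: 0.20/√(2 × 0.80/210) = 0.20/0.0873 = 2.29; Φ(2.29 - 1.97) is about 0.63.

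Simulated bootstrap rules gave 21-22% and 54-61%. Correlation between the predictors lowers this: over ρ from 0 to 0.5 a simulated direct contrast had power of 13-20% and 37-62%.

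**The case against.** A reader might infer that the plan will declare Hypothesis IV supported whenever disability is significant. The documents do not say so. Section 2.9 describes the task only as testing for covariate effects and states no decision rule. The over-reading is a risk, not a planned step.

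A reader might also infer that F tests can say nothing about order. That goes too far. Section 2.9 tests several covariates, and for single-degree-of-freedom terms in one ordinary regression, ordering by F is the same as ordering by the drop in explained variance. An informal point ordering would be available if the rivals were in the model. It would be unplanned, would carry no measure of uncertainty, and could change with which covariates are chosen afterwards.

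The high percentages are one end of a wide range, as the table shows. The simulation is a cross-sectional regression with two continuous predictors and no arms, repeated visits or missing data, so it is not the planned mixed model. Eligibility restricts mRS to 2-4 and enrolment to the early sub-acute phase, so disability and time since stroke both have limited spread.

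Finally, the first clause of Hypothesis IV is prognostic. The second clause, on rehabilitation content, is covered by the group and interaction tests. These objections narrow the consequence; they do not supply the missing comparison.

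**Conclusion.** The mismatch stands on the text alone: the hypothesis is a ranking, and the assigned test is of a non-zero effect. What is missing is a closed list of rivals, a comparison with its uncertainty, and a criterion for *most important*. A significant F test would support at most the statement that admission disability is a predictor.

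How often this would mislead cannot be fixed from the documents. With disability truly second and 210 patients, the assumed settings give significance in roughly 25-31% of trials (0.10 v 0.20) up to 95-98% (0.25 v 0.35).

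Nothing here touches the randomised comparisons, the primary-outcome analyses or the sample size. The point is minor.

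**What to change.** Choose one of two routes before the data are analysed.

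**Reword.** Change the first clause of Hypothesis IV to say that admission disability is a predictor of improvement. This is the cheapest route.

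**Keep the ranking and specify it in section 2.9:**

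- One disability measure: admission mRS. NIHSS is a separate rival, since section 2.4 treats it as neurological impairment.
- A closed list of rivals already collected, for example days since stroke, age, NIHSS, pre-stroke mRS, MoCA and NEO-FFI. Enter the NEO-FFI factors singly or use a measure adjusted for degrees of freedom, because a five-factor block would otherwise gain from its size.
- Association with change in the primary outcomes: predictor-by-measurement terms in the planned mixed model, or change at a fixed visit.
- An importance measure comparable across degrees of freedom, with bootstrap intervals for disability minus the best rival.
- Results with and without the outcome's own baseline. Baseline WHODAS is itself a disability score, so adjusting for it removes part of what is being ranked.
- A rule: say *most important* only if the interval lies above zero; otherwise say *a predictor*.

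Either route needs no new data; the second costs SAP text and computing. Its drawback is low power: about 20% for 0.40 v 0.30 and 54-61% for 0.40 v 0.20 with uncorrelated predictors. The weaker conclusion is therefore likely even if the hypothesis is true, and the SAP should say so.
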